3. STUDY DESIGN

The study will be a multicenter, randomized, double-blind, placebo-controlled trial to evaluate the efficacy and safety of NTZ for post-exposure prophylaxis of COVID-19 and other VRIs in elderly LTCF residents.

Subjects will be randomized within strata 1:1 to one of the following groups:

- Group 1 (NTZ): Two NTZ 300 mg tablets b.i.d. for 6 weeks
- Group 2 (Placebo): Two placebo tablets b.i.d. for 6 weeks

This study is expected to run from April 2020 through December 2020.

Rationale for important issues in the study design is described below:

- *Rationale for study design.* *In vitro* data suggest NTZ may be effective against the most common viruses associated with VRIs including SARS-CoV-2. Except for influenza, there are no drugs or vaccines commercially available to prevent VRIs, especially pandemic and outbreak strains of non-influenza viruses like SARS-CoV-2. In the case of influenza these drugs are limited to only the neuraminidase inhibitors for chemoprophylaxis and the vaccine has been demonstrated to be less effective in elderly patients. This study is designed to determine if a drug with broad-spectrum antiviral activity like NTZ can prevent VRIs in at risk elderly subjects residing in LTCFs.
- *Choice of NTZ dose and duration of treatment.* The dose of NTZ was selected based upon safety, tolerability and pharmacokinetics data from prior clinical experience with nitazoxanide. Extended release tablets at a dose of 600 mg administered twice daily with food will be used to achieve and maintain steady state plasma concentrations of tizoxanide above the concentrations required to inhibit respiratory viruses in cell cultures. The tablets will be administered with a B complex vitamin (Super B-Complex™, Igennus Healthcare Nutrition, Cambridge, UK) to mask potential chromaturia that may be observed due to the yellow color of nitazoxanide metabolites. A treatment duration of 6 weeks is expected to be sufficient to capture transmission of COVID-19 yet short enough to avoid unnecessary exposure to the medication. Studies of oseltamivir for prophylaxis of influenza in the LTCF population have employed a 6-week treatment duration. That treatment duration is supported by safety data from prior studies of NTZ and past experience noting prolonged activity of non-influenza viruses that extended for several months ([Monto et al. 1987](#), [Peters et al. 2001](#), [Falsey et al. 2008](#), NTZ 300 mg Tablets Investigators Brochure).
- *Choice of control groups.* A placebo control is appropriate for the study due to lack of any approved active control.
- *Choice of patient population.* The population to be studied is at high risk for COVID-19 and other VRIs and related complications and are likely to derive the most benefit from chemoprophylaxis. COVID-19 has been associated with high rates of mortality in this population, and therefore, effective post-exposure prophylaxis is needed ([McMichael et al. 2020](#)). There are no approved antivirals or vaccines for the prevention of non-influenza respiratory viruses, subjects will not be prevented from being prescribed rescue medication for complications if warranted. Therefore, participation in the study will not pose unreasonable risk to any eligible subject.
- *Choice of Vitamin B Complex Supplement.* All subjects will receive a vitamin B complex supplement [REDACTED] one tablet twice a day with study medication. This dose follows the manufacturer's labeled dosing. The purpose of the supplement is to help mask any chromaturia attributed to

NTZ and aid in maintaining study blinding. The supplement will supply each subject with the following Percent Daily Values based on a 2,000 calorie diet: vitamin B1 1,333%, vitamin B2 824%, vitamin B3 240%, vitamin B5 360%, vitamin B6 1000%, vitamin B7 100%, vitamin B12 15,000%, folate 100%, and vitamin C 267%. Considering this supplement will provide well beyond the needed daily allowance of these water-soluble vitamins, excess amounts are expected to be excreted in the urine and provide discoloration.

- *Choice of Patient-Reported Outcome Instrument.* This clinical trial will use the InFLUenza Patient-Reported Outcome Questionnaire (FLU-PRO[®]).

FLU-PRO[®] was developed with the support of the U.S. Department of Health and Human Services through the National Cancer Institute and the National Institutes of Allergy and Infectious Diseases, National Institutes of Health, in response to the need for improved metrics to evaluate treatment effect in clinical trials of drugs for the treatment of influenza and other respiratory tract viral diseases. It was developed and validated in accordance with FDA's guidance, "Patient-Reported Outcome Measures: Use in Medical Product Development to Support Labeling Claims." FLU-PRO[®] was separately validated for use in a population with non-influenza like illness and also has recently been used in vaccine studies with older adults for the prevention of RSV ([Powers et al. 2018](#), [Yu et al. 2020](#)).

- *Choice of ARI Definition.* The primary endpoint of this trial requires a determination that an ARI has occurred. We have defined ARI as " ≥ 0.5 increase from baseline in mean symptom score for the chest/respiratory FLU-PRO domain or ≥ 0.5 increase from baseline in mean symptom score for at least two of the following FLU-PRO[®] domains: body/systemic, nose, throat." In arriving at this definition, we reviewed published mean FLU-PRO[®] symptom score data over the course of RSV illness ([Yu et al. 2020](#)) as well as data from recently completed clinical trials in approximately 3,000 subjects with colds and influenza (Romark, data on file). The ARI definition requires an increase in symptom scores from baseline, although the magnitude of the required increase (≥ 0.5) in mean domain scores is low, and we are requiring that the increase in mean score be achieved for only one or two of the four domains.

4. SUBJECT SELECTION

The criteria for inclusion and exclusion are defined below:

4.1. Inclusion Criteria

1. Male and female residents of LTCFs at least 55 years of age.
2. Willing and able to provide written informed consent and comply with the requirements of the protocol.
3. At least one symptomatic laboratory-confirmed COVID-19 illness identified among residents or staff of the LTCF within 10 days prior to randomization.

4.2. Exclusion Criteria

1. Alzheimer's disease, dementia, or other mental incapacity which precludes comprehension of the study requirements or symptom diary.
2. Subjects expected to require hospitalization within the 8-week treatment and follow-up period.
3. Subjects with a history of COVID-19 or known to have developed anti-SARS-CoV-2 antibodies.
4. Subjects who experienced a previous episode of acute upper respiratory tract infection, otitis, bronchitis or sinusitis or received antibiotics for these conditions or antiviral therapy for influenza within two weeks prior to and including study day 1.
5. Receipt of any dose of NTZ within 7 days prior to screening.
6. Treatment with any investigational drug or vaccine within 30 days prior to screening or unwilling to avoid them during the course of the study.
7. Known sensitivity to NTZ or any of the excipients comprising the study medication.
8. Subjects unable to swallow oral tablets or capsules.
9. Subjects taking medications considered to be major CYP2C8 substrates, refer to [Table 7](#).
10. Subjects who, in the judgment of the Investigator, will be unlikely to comply with the requirements of this protocol.

5. STUDY PROCEDURES

All study visits are to occur in the subject's home facility.

5.1. Screening Evaluation (Day-90 to Day 1)

Before screening, subjects will be informed of the nature of study, and written consent must be obtained prior to participation. After giving informed consent, the subject will be assigned a subject number, and the following procedures will be carried out:

1. Complete medical history.
2. Physical examination including body weight and vital signs (blood pressure, pulse, respiratory rate and body temperature).
3. Collection of demographic information and smoking history.
4. Evaluation according to eligibility (inclusion and exclusion) criteria.

The information collected during the screening period must be current through the time of randomization.

5.2. Baseline (Day 1, may be same day as screening evaluation)

At baseline, the following procedures will be carried out:

1. Collection of two nasopharyngeal swabs (one from each nostril) using nylon flocked dry swabs for RT-PCR.
2. Collection of blood sample for laboratory safety tests and anti-SARs-CoV-2 antibodies.
3. Collection of a urine sample for routine urinalysis (appearance, glucose, protein and blood).
4. Review and recording of any concomitant medications.
5. Complete baseline symptom diary entries.
6. Randomization and dispensing of study medication (medication assigned in sequential order).
7. Administration of the first dose of study medication with food (< 1 hour after food intake) and a B complex vitamin (███████████) ██████ under observation of Investigator or a member of Investigator's staff, and entry in the medication administration record.
8. Instruct subject regarding:
 - a. *Administration of study medication.* Subjects will be instructed to take the study medication (two tablets) and a B complex vitamin (███████████) ██████ twice daily with the morning and evening meals, approximately every 12 hours (< 1 hour after food intake, preferably a high-fat meal but at a minimum a cereal bar).
 - b. *Follow-up visits:* Subjects will be instructed on the study schedule and follow up visits at Week 1, Week 3, Week 6 and Week 8.
 - c. *Seeking emergency care or contacting the study physician or nurse:* Subjects must be informed to seek emergency medical care or contact the study physician or nurse if they develop any of the following symptoms listed below during the full 8-week study and follow-up period.

CONTACT STUDY PHYSICIAN, IF:

- Trouble breathing including shortness of breath
- Severe headache, stiff neck, confusion or excessive somnolence
- If fever ($\geq 99^{\circ}\text{F}$ or $\geq 37.2^{\circ}\text{C}$) returns after being absent for 24 hours
- Increased difficulty breathing
- Wheezing develops
- New pain develops or pain localizes to one area, such as an ear, the throat, the chest, or the sinuses
- Symptoms become more severe or frequent
- Symptoms recur or any difficulty breathing following 5-10 days resolution of illness
- An allergic-like reaction occurs or is suspected
- Abnormal behavior

5.3. Daily Day 1 through Week 6

A caregiver will record the time of each study medication intake. Once daily, the caregiver will (i) inquire regarding the health of the subject, (ii) record any concomitant medications, and (iii) ask the subject once daily, “do you feel like you have symptoms of a cold or flu?” If the subject responds “yes”, the caregiver will have the subject complete a FLU-PRO® diary to evaluate the subject’s symptoms. If the subject reports (i) at least one of the Lower Respiratory Symptoms presented in [Table 5](#) below or (ii) at least one symptom from each of the Upper Respiratory Symptoms and Systemic Symptoms categories presented in [Table 5](#) below, the caregiver will then contact the study physician or nurse to complete a “Suspected ARI Visit” with the procedures provided below.

Table 5: Clinical Symptoms Required for Suspected ARI¹ (adapted from [Yu et al. 2020](#))

Upper Respiratory Symptoms	Lower Respiratory Symptoms	Systemic Symptoms

 • Nasal congestion/rhinorrhea (runny or dripping nose, congested or stuffy nose, head congestion, sinus pressure)² • Sore throat (sore or painful throat)² 	
 • Cough (coughing, chest congestion, chest tightness, dry or hacking cough, wet or loose cough)² • Dyspnea (shortness of breath)² • Sputum (coughing up sputum or phlegm)² • Wheezing 	
 • Myalgias or arthralgias (body aches or pains)² • Fatigue (weak or tired, sleeping more than usual)² • Headache • Decreased appetite (lack of appetite, did not feel like eating)² • Feverishness (felt hot, chills or shivering, felt cold, sweating)²

¹ Suspected ARI requires self-reporting of any Lower Respiratory Symptom, or at least one Upper Respiratory Symptom together with one Systemic Symptom.

² Lay language used in the FLU-PRO® questionnaire is presented in parentheses.

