1. INTRODUCTION

1.1. Viral Respiratory Illnesses in Long-Term Care Facilities

Respiratory tract infections result in approximately 4 million deaths globally each year. The elderly population is at disproportionate risk due to age-related characteristics such as frailty and immunosenescence. Moreover, this population experiences more severe illnesses, a larger number of hospitalizations and greater mortality rates. The elderly population is growing rapidly and will double by 2050. LTCFs are an important subset of the elderly population, in developed countries approximately 5% live in these facilities. LTCF residents are at elevated risk of acquiring respiratory tract infections due to elevated infection rates, which may be amplified in part due to close living conditions (Childs et al. 2019, McGeer et al. 2000).

An array of viral respiratory pathogens occur in this population, including coronaviruses, RSV, rhinoviruses and hMPV, with infections occurring in as many as 41% of LTCF residents surveyed (Falsey et al. 2008, Checovich et al. 2020). Rhinoviruses have been associated with as much as 59% of LTCF outbreaks and may result in severe disease (Longtin et al. 2010). RSV and hMPV are widely reported to circulate during an influenza season, with RSV infections occurring at 4 times the rate of the general population in the elderly (Ursic et al. 2016, Thompson et al. 2003). Outbreaks of seasonal strains of coronavirus have been reported, with the potential to cause severe respiratory illness (Hand et al. 2018). Furthermore, outbreaks of SARS-CoV-2 in LTCFs have been associated with widespread infection amongst residents and high mortality rates (McMichael et al. 2020, Kimball et al. 2020).

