8.3. Response Definitions

ARI:	≥ 0.5 increase from baseline in mean symptom score for the chest/respiratory FLU-PRO domain or ≥ 0.5 increase from baseline in mean symptom score for at least two of the following FLU-PRO [®] domains: body/systemic, nose, throat.
COVID-19:	ARI after start of treatment and before the end of the 6-week treatment period associated with detection of SARS-CoV-2 by RT-PCR assay of nasopharyngeal swab.
VRI:	ARI after start of treatment and before the end of the 6-week treatment period associated with detection of any respiratory virus by RT-PCR assay of nasopharyngeal swab.

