### Suspected ARI Visit

Subjects reporting any lower respiratory symptom or at least one upper respiratory symptom and one systemic symptom are considered to have a suspected acute respiratory illness (ARI) and will complete the following procedures at an unscheduled Suspected ARI Visit.

1. Physical examination as warranted by the Investigator for any change from baseline.
2. Body weight and collection of vital signs to include blood pressure, pulse, respiratory rate and body temperature.
3. Collect two nasopharyngeal swabs using nylon flocked dry swabs for RT-PCR at the Suspected ARI Visit.
4. Collect two nasopharyngeal swabs 24 to 36 hours later, and then again 4 to 5 days later.

5. The subject will complete a FLU-PRO® symptom diary daily until he/she responds "yes" to the FLU-PRO® question, "Have you returned to your usual health?" for 3 consecutive days or until the Week 6 Visit, whichever occurs first. The daily FLU-PRO® diary will be completed between 4:00 pm and 8:00 pm. A caregiver may assist the subject with completing the diary if necessary.
6. Review and recording of concomitant medications.
7. Review and recording of adverse events/side effects.
8. Laboratory investigations for safety may be performed as warranted based upon the Investigator's judgment.
9. Subjects testing positive for a respiratory virus by RT-PCR may receive standard of care as clinically warranted by the Investigator.

Regardless of symptoms or laboratory data, the subject will continue treatment until the 6-week treatment period has ended.

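### An illness confined to nose and throat can meet the ARI definition without requiring a swab, so its ascertainment for both primary endpoints is discretionary

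*Protocol*

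**What the plan says.** **ARI definition.** Protocol Section 8.3 and SAP Section 4.1 give two routes. One is a rise of at least 0.5 in the chest/respiratory domain. The other, with the same threshold, asks for an "increase from baseline in mean symptom score for at least two of the following FLU-PRO" scales; the list given there reads "domains: body/systemic, nose, throat".

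**Endpoints.** Section 8.3 defines COVID-19 and VRI as an ARI associated with RT-PCR detection on a nasopharyngeal swab. It does not say at which visit the swab must be taken.

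**Swab trigger.** Under Protocol Section 5.3, when a subject reports cold or flu symptoms at the daily check, the first step is that "the caregiver will have the subject complete a FLU-PRO" questionnaire. The visit rule is then applied: without a lower respiratory symptom, it needs "at least one symptom from each of the Upper Respiratory Symptoms and Systemic Symptoms categories". Footnote 1 of Table 5 puts the whole rule as follows: "Suspected ARI requires self-reporting of any Lower Respiratory Symptom, or at least one Upper Respiratory Symptom together with one Systemic Symptom". Table 5 lists nasal symptoms and sore throat together in the upper respiratory column. SAP Section 1.2 has the same rule, in a sentence that begins "Subjects reporting any lower respiratory symptom or at least one upper respiratory symptom and one systemic symptom are considered to have a suspected acute respiratory".

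**Other routes to a swab.** Protocol Section 5.10 allows swabs at the investigator's discretion. Section 5.7 lists them among optional procedures at unscheduled visits. The Synopsis mentions investigator swabs at visits for COVID-19 or VRI symptoms. A row of Table 9 can be read as referring every subject who reports cold or flu symptoms. After baseline, no swabs are scheduled at Weeks 1, 3, 6 or 8.

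**The concern.** The trigger decides who must be tested, and the ARI definition decides who can count. If an illness can satisfy the second without the first, the plan does not guarantee the virology that its own endpoint needs. Protocol Section 3 explains that the ARI threshold was set low and that a rise in only one or two domains is enough. No reason is given for leaving one qualifying pair outside mandatory testing.

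For that pair, whether a true event is found depends on the judgement of individual investigators, and on whether the site works from Section 5.3 or from Table 9. Practice may therefore differ by facility. Events missed in both arms reduce power on both primary endpoints. The SAP also does not say what becomes of an ARI with no swab result.

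**Working it through.** **Step 1: compare the two rules.** Take chest, body/systemic, nose and throat as present or absent, giving 16 patterns. Assume that a chest rise implies a Table 5 lower respiratory symptom and that a body/systemic rise implies a Table 5 systemic symptom. The documents do not map domains to Table 5 item by item.

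- ARI: chest present gives 8 patterns. Chest absent with at least two of the other three gives 4. Total 12.
- Trigger: chest present gives 8. Chest absent, body/systemic present, and nose or throat present gives 3. Total 11.
- ARI without trigger: one pattern, nose plus throat alone.
- Trigger without ARI: none at this level.

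In severity the trigger is the looser rule, since any reported symptom suffices and no 0.5 rise is needed.

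**Step 2: reproduce the plan's power.** Inputs (Protocol Section 8.1, SAP Section 1.3): 400 per arm; COVID-19 5% versus 1%; VRI 10% versus 2%; two-sided tests. Expected events are 400 × 0.06 = 24 and 400 × 0.12 = 48.

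Without continuity correction, power = Φ[(|p1 − p2|√n − z√(2p̄(1 − p̄))) / √(p1(1 − p1) + p2(1 − p2))].

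- COVID-19, alpha 0.049: (0.8 − 1.9685 × 0.2412) / 0.2396 = 1.357, so 91.3% (Protocol: 92.8%).
- VRI, alpha 0.001: (1.6 − 3.2905 × 0.3359) / 0.3311 = 1.495, so 93.3% (Protocol: 93.9%).

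With continuity correction and 20 equal strata, as SAP Section 4.2.1 plans, power = Φ[(D − 0.5 − z√V0) / √V1]. Here D = 400|p1 − p2|/2, V0 is the CMH null variance and V1 the variance under the alternative.

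- COVID-19, alpha 0.047: (7.5 − 1.986 × 2.443) / 2.396 = 1.105, so 86.5% (SAP: 87.1%).
- VRI, alpha 0.001: (15.5 − 3.2905 × 3.401) / 3.311 = 1.301, so 90.3% (SAP: 91%).

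The stated figures reproduce to within 2 points. Direct simulation of the corrected CMH test (200,000 trials, 20 strata of 40) gives 90.1% and about 94%, somewhat above the SAP's figures.

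**Step 3: illustrate the loss.** Let f be the share of true events missed, equal in both arms. This is an assumption; the documents give no value. Both rates are multiplied by (1 − f), and the corrected CMH test is simulated again.

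| f | COVID-19 events | COVID-19 power (alpha 0.047) | VRI events | VRI power (alpha 0.001) |
|---|---|---|---|---|
| 0 | 24.0 | 90% | 48.0 | 94% |
| 5% | 22.8 | 88% | 45.6 | 92% |
| 10% | 21.6 | 86% | 43.2 | 89% |
| 20% | 19.2 | 81% | 38.4 | 82% |
| 30% | 16.8 | 74% | 33.6 | 72% |

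Here f means events actually missed after any discretionary swabbing or later trigger, so it is at most the share of illnesses confined to nose and throat.

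**The case against.** The strongest reply is that the gap is narrow and has several ways out.

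- The trigger covers 11 of the 12 patterns and is looser on severity. One report of cough, fatigue, headache, poor appetite or aches alongside a nasal or throat symptom is enough.
- The daily question is repeated and each positive answer leads to a diary, so the rule is re-applied on every symptomatic day.
- Section 5.2 also tells subjects to contact the study physician about new pain, including in the throat or sinuses.

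All of this stands, and it limits the size of the problem. It does not close the gap, because none of these routes makes a swab mandatory under Section 5.3 for an illness that stays in the nose and throat. Table 9 does not settle the matter: its footnote 6 refers back to the Suspected ARI criteria.

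A reader might infer that such an illness is never swabbed and can never count. The documents do not support that, since a positive swab from any visit would satisfy Section 8.3. A reader might also infer that the subject is scored VRI-negative; neither document says so. Nor does the diary necessarily stop, given the daily question.

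On size, the 10% VRI rate is a planning assumption, and the documents do not say whether it is before or after ascertainment loss, so reducing it further may count the loss twice. At f of 5% to 10%, the simulated VRI power of 92% to 89% lies around the SAP's stated 91%. The statement in Protocol Section 1.1, "Rhinoviruses have been associated with as much as 59% of LTCF outbreaks", concerns which virus is found in outbreaks. It says nothing about how often illness stays in the nose and throat.

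**Conclusion.** The mismatch is real, is the same in Protocol and SAP, and affects both primary endpoints, but only for one symptom pattern. For that pattern a swab is not mandatory, so ascertainment is discretionary and may differ by facility. The size cannot be fixed from the documents. The power range above is an illustration that rests on assumed shares, equal loss in both arms and the plan's event rates.

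Equal loss costs power but does not inflate type I error. Because randomisation and the CMH test are both stratified by facility, differences in swabbing between facilities would not by themselves confound the treatment comparison. A reader might go further and suspect bias in favour of nitazoxanide: Protocol Section 1.2.1 describes cytokine suppression, and fewer systemic symptoms could move treated infections into the unswabbed pattern. That is a possibility only; nothing in the documents shows it.

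The change is worth making because it is specific and cheap, not because a large loss has been shown.

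**What to change.** 1. In Protocol Section 5.3, Table 5 footnote 1 and SAP Section 1.2, keep the present trigger and also make swabs mandatory when symptoms fall in both the nose and throat domains. Alternatively, add swabs whenever a diary meets the ARI definition; this needs the diary to be scored against baseline promptly.
2. Reconcile the referral row of Protocol Table 9 with Section 5.3, so that every site follows one rule.
3. State in the SAP whether an ARI with no swab is a missing endpoint, and so enters the best-case, worst-case and tipping-point analyses of Section 2.3, or a non-event.

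The cost is a short amendment and some additional Suspected ARI Visits, each with the initial swabs and two repeat collections. These use swabs, laboratory and staff already in place. The third item is a change of SAP text only.
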